## **METHODS:**

Informed consent will be obtained at the study site at the time of the first consultation for participation in this study.

After providing informed consent, subjects will be assessed for study eligibility at the Screening visit (day -28 to day -1). At the Screening visit the following procedures will be performed:

1. Medical history and concomitant as well as prior medications/treatments will be reviewed
2. Skin examination will be performed (including assessment of PASI, sPGA, and BSA)
3. Approximately 14 cc (approximately 3 teaspoons) of blood will be drawn for a complete blood count (including differential) (not required if subject can provide results from a previous test performed within 4 months of screening visit).
4. Approximately 5 cc (approximately 1 teaspoon) of blood will be drawn for a QuantiFERON TB-Gold test (QFT) assay; or subjects will undergo tuberculin purified protein derivative (PPD) testing (not required if subject can provide results of a negative test performed within 8 months of screening visit).
5. Females of child bearing potential will have 5 cc (approximately 1 teaspoon) of urine collected for a pregnancy test. This test must be negative in order to qualify for the study.

Subjects will be deemed eligible as per inclusion/exclusion criteria. Qualified subjects meeting all the inclusion and exclusion criteria will be start treatment at Day 0/Baseline (within 28 days of signing the consent form). Female subjects of child-bearing potential will have 2 teaspoons of urine collected for a pregnancy test prior to treatment. This test must be negative in order to continue to qualify for the study. Assessments at this Day 0/Baseline visit include skin examination with assessment of PASI, sPGA, and BSA scores.

Subjects will receive brodalumab (210 mg) via subcutaneous injection using prefilled syringes at Weeks 0, 1, 2, and every 2 weeks thereafter through and including Week 16. Patients will be taught how to administer the drug subcutaneously by a study investigator or designated research staff member at the Baseline visit. They will be dispensed a one-month supply of medication at baseline and each subsequent visit for self-administration at home.

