At Weeks 4, 8, 12 and 16 subjects will return for assessment of concomitant medications and adverse events, and skin assessments including PASI, sPGA, BSA scores, and photography of target lesion(s). In addition, females of child-bearing potential will have 2 teaspoons of urine collected for a pregnancy test at each visit.

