**Exclusion criteria:**

1. Have predominantly pustular, erythrodermic, and/or guttate forms of psoriasis.
2. History of an ongoing, chronic or recurrent infectious disease, or evidence of tuberculosis infection as defined by a positive tuberculin purified protein derivative (PPD) or QuantiFERON TB-Gold test (QFT) at Screening. Subjects with a positive or indeterminate PPD or QFT test may participate in the study if a full tuberculosis work up (according to local practice/guidelines) is completed within 12 weeks prior to randomization and establishes conclusively that the subject has no evidence of active tuberculosis. If presence of latent tuberculosis is established, then treatment must have been initiated at least for 4 weeks prior to randomization and the course of prophylaxis is planned to be completed.
3. Subjects with a history of HIV, or history of positive HCV or HBV
4. Use of any of the following therapies within 4 weeks prior to Baseline (Visit 2): systemic non-biologic psoriasis therapies (including, but not limited to): psoralens and ultraviolet A (PUVA) therapy, cyclosporine, methotrexate, azathioprine, corticosteroids, apremilast, tofacitinib, oral retinoids, mycophenolate mofetil, sirolimus; 1, 25 dihydroxyvitamin D analogs; or phototherapy (including UVB or self-treatment with tanning beds or therapeutic sunbathing) or topical psoriasis therapy with psoralens.
5. Use of topical corticosteroid preparations, topical calcineurin inhibitors, or other topical preparations with immunomodulatory properties within 2 weeks prior to Baseline (Visit 2).

6. Use of any investigational drug or any systemic drug for psoriasis within four weeks prior to Baseline (Visit 2).
7. Serious concomitant illness that could require the use of systemic corticosteroids or otherwise interfere with the patient's participation in the trial.
8. Clinically important deviation as judged by the investigator (such WBC< 3) from normal limits in physical examination, vital sign measurements, clinical laboratory tests results, not associated with a chronic, well-controlled medical condition.
9. Any active live-vaccines 3 months prior to baseline and throughout the study.
10. Have a current or history of lymphoproliferative disease within 5 years prior to Baseline (Visit 2); or have current or history of any malignant disease within 5 years prior to Baseline (Visit 2).
11. History of suicide attempt, or are clinically judged by investigator to be at risk of suicide.

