#### **ADVERSE EVENTS:**

As of July 19, 2016, the brodalumab safety package across multiple indications included 6243 brodalumab-treated patients. The majority of patients were followed for 1 to 2 years, with 102 having follow up for over 5 years. The safety profile of brodalumab in psoriasis patients include 4464 patients, using integrated safety data from the phase 2 and phase 3 trials, and their open-label extensions. Overall, the safety profile of brodalumab was found to be consistent with other biologic agents targeting the IL-17 pathway.

The most common adverse events ( $\geq 2\%$  of patients) in patients exposed to brodalumab 210 mg q2w were nasopharyngitis, upper respiratory tract infection, arthralgia, and headache. Adverse drug reactions include headache, arthralgia, fatigue, oropharyngeal pain, diarrhea, nausea, myalgia, influenza, injection site reactions, neutropenia, and tinea infections, conjunctivitis, and candida infections.

Through the end of the psoriasis studies, a total of 23 deaths were reported among the patients who received brodalumab. This includes a total of 4 completed suicides, including one reported as an intentional overdose. There was no increase in overall risk of death above what would be expected in the patient population.

There were no differences in the rates of serious adverse events at week 12 of treatment between brodalumab, ustekinumab, or placebo. Overall, the rates of adverse events leading to discontinuation of treatment were low and comparable to placebo at week 12 and ustekinumab at week 52, with no increase through the long term period. Serious adverse events with incidence rates  $\geq 0.1\%$  in the brodalumab patients at week 12 were cellulitis, appendicitis, gastroenteritis, and acute pancreatitis. Major Adverse Cardiovascular Events (MACE) were reported at 0.2% at 12 weeks in brodalumab exposed patients, and 0.61 per 100 patient years in the all-brodalumab group at week 52 as compared to 0.40 in the ustekinumab group. The sponsor concluded that there was no evidence for a causal association between MACE and brodalumab.

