Other identified and potential risks of brodalumab treatment include: worsening of Chron's disease; higher rate of infections with the majority reported as nonserious, mild, and self-limited; neutropenia at a rate of 0.7% in the 12-week trial, with most cases reported as transient and reversible; hypersensitivity at a rate of 1.7% for brodalumab 210 mg q2w; and malignancy, with exposure-adjusted event rates at 52 weeks of 0.3 in the all-brodalumab group as compared to 0.4 in the ustekinumab group, with no increase over long term follow up. [5, 6]

Brodalumab was FDA-approved in February, 2017 with a Risk Evaluation and Mitigation Strategy to ensure that prescribers and patients are aware of the risk of suicidal ideation. Investigators will be REMS certified and Study Subjects will sign the Patient-Prescriber Agreement Form prior to initiating study drug.

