## **SAFETY MONITORING**

The study will be conducted in accordance with our department's Standard Operating Procedures, which are based on US FDA Title 21 Code of Federal Regulations and ICH Good Clinical Practice guidelines.

An investigator will review all laboratory results and assess for adverse events. The principal investigator will be informed of all adverse events. In the event that a subject's safety is compromised, the investigator will discontinue the subject immediately.

A DSMB will be formed and will be comprised of two board certified dermatologists experienced in prescribing biologic treatments. All SAEs will be reported to the DSMB board within 24 hours of our being informed of the event. In addition, the DSMB will receive a compiled list of all related adverse events, from all sites, every three months, so that they can determine if the risks have changed and whether or not the study should continue as planned.

**Definition of an AE:** Any untoward medical occurrence in a subject administered a pharmaceutical product that does not necessarily have a causal relationship with the treatment. An AE can therefore be any unfavorable and unintended sign (including an abnormal laboratory finding), symptom, or disease temporally associated with the use of a medicinal (investigational) product, whether or not considered related to the investigational medicinal product.

Investigational Medicinal Product (IMP) includes the drug under evaluation and the comparator drug(s) if specified as part of the research objective, given at any time during the study. Medical conditions/diseases present before starting the drug of interest are only considered adverse events if they worsen after starting the drug of interest.

The occurrence of adverse events will be sought by non-directive questioning of the patient at each visit during the study. Adverse events also may be detected when they are volunteered by the patient during or between visits or through physical examination, laboratory test, or other assessments. All adverse events will be recorded in the study database including the following information:

1. the severity grade (mild, moderate, severe)
2. its relationship to the drug(s) of interest (suspected/not suspected)
3. its duration (start and end dates or if continuing at final exam)
4. whether it constitutes a serious adverse event (SAE)

A SAE is any untoward medical occurrence that at any dose:

- results in death,
- is life-threatening,

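### Suicidal ideation is the named REMS risk, but no directed question on it is scheduled before drug is re-supplied at Weeks 4, 8 and 12

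*Combined protocol and SAP*

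**What the plan says.** **The risk is named.** ADVERSE EVENTS says that brodalumab was approved with a "Risk Evaluation and Mitigation Strategy to ensure that prescribers and patients are aware of the risk of suicidal ideation". The same section reports 23 deaths among brodalumab patients through the end of the psoriasis studies and adds: "This includes a total of 4 completed suicides, including one reported as an intentional overdose". It also says that overall mortality was no higher than expected for the population.

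**It is handled at entry.** Exclusion criterion 11 reads: "History of suicide attempt, or are clinically judged by investigator to be at risk of suicide". Appendix A marks the eligibility check at V1 and V2 only. Investigators are to be REMS certified, and each subject signs the Patient-Prescriber Agreement before the first dose (a V2-only row in Appendix A).

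**On treatment the enquiry is open-ended.** SAFETY MONITORING states: "The occurrence of adverse events will be sought by non-directive questioning of the patient at each visit during the study". It then allows for events that patients volunteer, or that come to light through examination, laboratory tests or other assessments. METHODS says: "At Weeks 4, 8, 12 and 16 subjects will return for assessment of concomitant medications and adverse events", followed by skin scores, photographs and a pregnancy test. Appendix A matches this and has no row for mood or suicidality.

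**Drug goes home monthly.** METHODS: "They will be dispensed a one-month supply of medication at baseline and each subsequent visit for self-administration at home". Appendix A marks dispensing at V2 to V5 (Weeks 0, 4, 8 and 12).

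**The concern.** The protocol judges suicide risk serious enough to exclude on, yet no scheduled item calls for that judgement to be repeated once a subject is on the drug. The visits at Weeks 4, 8 and 12 are the planned occasions on which an investigator could learn of ideation before releasing another month's supply.

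The protective rules elsewhere depend on someone already knowing. If safety is compromised, "the investigator will discontinue the subject immediately"; EARLY TERMINATION has a similar rule for any threat to well-being. Neither can act on ideation that has not been disclosed or noticed. What is at stake is the protection of individual subjects, not the estimate of efficacy.

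**Working it through.** The plan states no figure on this point, so there is none to reproduce. The check compares sections, counts doses and puts the background risk in proportion.

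**1. What each safeguard does on treatment**

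| Safeguard | Section | Does it prompt enquiry at Weeks 4 to 16? |
|---|---|---|
| Exclusion criterion 11 | Exclusion criteria; Appendix A | No; eligibility is checked at V1 and V2 |
| REMS certification and agreement form | ADVERSE EVENTS; Appendix A | Raises awareness, so makes volunteered reports more likely; no on-treatment enquiry described |
| Adverse-event questioning | SAFETY MONITORING | Yes, at every visit, but not directed at this risk |
| Discontinuation rules | SAFETY MONITORING; EARLY TERMINATION | No; they act once a threat is known |
| 24-hour SAE reports, three-monthly DSMB list | SAFETY MONITORING | No; they act on events already recorded |
| Questionnaires | EARLY TERMINATION | Unnamed, optional, and only for subjects who stop early |

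Pregnancy is a useful comparison inside the same protocol: a test at every visit from V1 to V6 and an explicit rule to stop.

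**2. Re-supplies affected**

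Dispensing visits after baseline are V3, V4 and V5. With 40 subjects, 3 × 40 = 120 at most (fewer if subjects stop early).

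**3. Doses carried by those re-supplies**

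METHODS gives brodalumab "via subcutaneous injection using prefilled syringes at Weeks 0, 1, 2, and every 2 weeks thereafter through and including Week 16". The doses therefore fall at Weeks 0, 1, 2, 4, 6, 8, 10, 12, 14 and 16. The baseline supply covers Weeks 0, 1 and 2. Weeks 4, 6, 8, 10, 12 and 14 come from V3 to V5. The source of the Week 16 dose is unclear, because Appendix A marks neither dispensing nor administration at V6.

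Appendix A also marks administration of study drug at V3, V4 and V5, so the number of doses injected at home depends on the reading:

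- Weeks 4, 8 and 12 given at the visit: home doses are Weeks 6, 10 and 14, so 3 per subject (3 × 40 = 120).
- All taken at home: 6 per subject (6 × 40 = 240).
- Week 16 taken from the Week 12 supply: add 1 per subject, giving 4 (160) or 7 (280).

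**4. Background risk of completed suicide**

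Inputs from ADVERSE EVENTS: 4 suicides and 4464 psoriasis patients. I assume that the 4 arose among the 4464.

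- Unscaled: 4 / 4464 = 0.000896; × 40 = 0.036, about 0.04.
- Scaled to 16 weeks, assuming 1 year of follow-up: 0.036 × 16/52 = 0.011.
- Scaled to 16 weeks, assuming 2 years: 0.036 × 16/104 = 0.006 (rounded up from 0.0055).

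The 1 to 2 years is an assumption. The protocol gives that follow-up for most of the wider 6243-patient safety package, not for the 4464. These are point estimates, and criterion 11 should lower the risk further. The documents give no rate of ideation.

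**The case against.** The strongest reply is that the protocol already adopts the mitigation that came with approval. Certified investigators know what to look for, subjects have been told of the risk and have signed to say so, at-risk subjects are excluded, and a subject may report ideation at or between visits. Nothing in the documents shows that one yes/no question would find ideation that this arrangement misses. The REMS content and the department's procedures are not in the documents and may already require the enquiry.

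Much of this stands. A reader might infer that non-directive questioning is the sole route of detection, or that no suicide-specific safeguard operates after entry. The text supports neither: SAFETY MONITORING lists other routes, and REMS awareness carries through treatment. A reader might also infer that every re-supplied dose is injected unsupervised at home; the administration marks at V3 to V5 could halve that count. Nor is 0.04 a ceiling, since it is a point estimate, though one not reduced to 16 weeks. The yield of the question cannot be quantified from these documents.

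What does not stand is that awareness amounts to enquiry. As described, the REMS steps are certification and a single signature at V2. They make disclosure more likely but leave it to the subject's initiative or to what the investigator notices, and practice may differ across 3 to 4 sites.

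**Conclusion.** The concern holds as a gap in scheduled safety enquiry. The protocol names suicidal ideation as the REMS risk and screens for suicide risk at entry, but requires no directed question about it on treatment. Up to 120 re-supplies, carrying 3 to 7 home doses per subject, are affected.

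The count of re-supplies rests on full enrolment and Appendix A's dispensing marks; the dose range reflects the unclear administration and Week 16 entries. The conclusion concerns what this protocol schedules; it does not say that investigators will fail to ask. If the REMS or a site procedure requires the question, the defect shrinks to a missing cross-reference and a missing record.

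It would go too far to conclude that a suicide is to be expected in this trial or that the efficacy result is compromised. The expected number is about 0.04 unscaled and roughly 0.006 to 0.011 on the scaling assumed above, and the primary endpoint is unaffected. The case for change rests on individual protection and low cost.

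**What to change.** - **Add the question.** In SAFETY MONITORING, and as a row in Appendix A, add one directed yes/no question on suicidal thoughts or behaviour, asked by existing staff before drug is dispensed at V3, V4 and V5. Asking it at V6/ET as a closing safety check is optional.
- **State the response to a yes.** Same-day assessment by the investigator, no dosing or dispensing until that is done, referral as needed, and consideration of discontinuation under EARLY TERMINATION.
- **If the enquiry already exists** in the REMS or a site procedure, cite it in SAFETY MONITORING and record the answer in the study database.

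**Cost.** 3 × 40 = 120 brief questions, or 4 × 40 = 160 with V6/ET; one data field; a referral route at each site; and a possible dose delay after a yes. If the study has started, it also needs a protocol amendment with IRB review at the 3 to 4 sites. No new visit, sample or staff is needed.

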- requires inpatient hospitalization or prolongation of existing hospitalization,
- results in persistent or significant disability/incapacity,
- is a congenital anomaly/birth defect,
- is otherwise a significant medical event.

This includes any SAEs likely to arise from the trial indication or progression of underlying/concomitant illness (es) (e.g. progression of cancer in oncology trials), unless specified in the protocol as study specific exemptions.

Any SAE, irrespective of causality, occurring after the subject has provided informed consent and until four weeks after the subject has stopped study participation must be reported unless otherwise stated in the protocol. SAEs occurring after four weeks from ending study participation should only be reported if considered by the Investigator

attributable to the exposure to the investigational drug(s) during the trial period. This includes the period in which the study protocol interferes with the standard medical treatment given to a subject, even if study treatment has not yet started (e.g. withdrawal of previous treatment during washout period, change in treatment to a fixed dose of concomitant medication).

**Timelines:** All serious adverse events (SAEs) from interventional clinical trials must be reported by the sites to the Lead PI within 24 hours of occurrence of the SAE and to the site's own IRB as required. The Lead PI will then report to the manufacturer and any other authorities.

**Follow-up reports:** All related SAEs will be followed until resolution or until it is judged to be permanent, and an assessment will be made at each visit (or more frequently, if necessary) of any changes in severity, the suspected relationship to the drug of interest, the interventions required to treat it, and the outcome.

**Pregnancies:** Any occurrences of a pregnancy in a patient (or a patient's partner) during study participation will be collected. All pregnancies will be followed up to determine outcome, including spontaneous or voluntary termination, details of the birth, and the presence or absence of any birth defects, congenital abnormalities, or maternal and/or newborn complications.

Should a temporary or permanent suspension occur, we would report the occurrence to all appropriate authorities.

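### Pregnancy aside, follow-up to outcome and re-assessment of causality are required only for SAEs already judged related, and completers have no scheduled contact in the four-week SAE reporting window

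*Combined protocol and SAP*

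**What the plan says.** SAFETY MONITORING treats reporting and follow-up separately.

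- **Reporting.** The obligation covers "Any SAE, irrespective of causality, occurring after the subject has provided informed consent and until four weeks after the subject has stopped study participation". After that, an SAE is reported only if the investigator attributes it to the study drug. Sites report to the Lead PI, and "The Lead PI will then report to the manufacturer and any other authorities". For the DSMB, "All SAEs will be reported to the DSMB board within 24 hours of our being informed of the event"; its three-monthly list is confined to related adverse events.
- **Follow-up.** Under Follow-up reports, "All related SAEs will be followed until resolution or until it is judged to be permanent". The rest of that sentence calls for severity, relationship, interventions and outcome to be reviewed at each visit, or more often if needed.
- **Recording.** Every adverse event, related or not, is entered with severity, relationship, seriousness and "its duration (start and end dates or if continuing at final exam").
- **Pregnancy.** "All pregnancies will be followed up to determine outcome", with no condition on relationship.
- **Elicitation.** "The occurrence of adverse events will be sought by non-directive questioning of the patient at each visit during the study". Events may also be volunteered, or come to light through examinations and tests.
- **Visits.** METHODS states: "At Weeks 4, 8, 12 and 16 subjects will return for assessment of concomitant medications and adverse events". The last column of Appendix A is V6/ET at week 16. EARLY TERMINATION asks subjects who leave early to attend one final visit, and gives no date for it.

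**The concern.** Reporting is blind to causality, but follow-up is not. The duty to re-assess relationship applies only where the answer is already that the event is related. The first judgement on an SAE is made when least is known about it. If that judgement is *not suspected*, nothing in the protocol requires it to be revisited, and no final outcome is required if the event is still open at the final exam.

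The second gap is one of detection. The protocol sets a four-week reporting window after participation but, for completers, schedules nothing in it.

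Safety is the secondary objective. The study is open-label with no control arm, so relationship judgements on individual events carry more weight than they would beside a comparator. The two gaps act differently. The follow-up rule leaves the SAE count unchanged but can leave relationship and outcome incomplete. The missing contact can lower the count itself.

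**Working it through.** **1. What is required for each kind of SAE (pregnancy outcomes aside)**

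| Requirement | Judged related | Judged not related |
|---|---|---|
| Initial report to Lead PI, manufacturer and DSMB | yes | yes |
| Severity, relationship and seriousness entered | yes | yes |
| End date, or continuing at final exam | yes | yes |
| Relationship re-assessed at visits | yes | not required |
| Followed until resolved or permanent | yes | not required |
| Included in DSMB three-monthly list | yes | no, unless upgraded |

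No other section supplies the two requirements missing from the right-hand column.

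**2. Timeline**

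- Last scheduled contact for a completer: week 16 (METHODS, Appendix A).
- End of the SAE window: 16 + 4 = week 20.
- Scheduled contacts after the week 16 visit up to week 20: 0.
- Share of the time from baseline to the end of the window: 4/20 = 20%.
- Early terminators: the window opens when participation stops and the final visit is undated, so that visit may fall inside the window. No contact is set for the window's end.

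The allowance for more frequent assessment applies to related SAEs already known. It cannot find a new one.

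**3. Upper limit on uncovered time**

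Inputs: 40 subjects (RESEARCH DESIGN) and 4 weeks (SAFETY MONITORING). Assumption: all 40 are uncovered for the whole window.

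- 40 × 4 = 160 person-weeks.
- 160 / 52.18 = 3.07 patient-years.

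**4. Events in that time**

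- Major adverse cardiovascular events at 0.61 per 100 patient-years (ADVERSE EVENTS, all-brodalumab group at week 52): 0.0061 × 3.07 = 0.019, about 0.02 events. This is one type of SAE only.
- All SAEs: the documents give no rate per patient-year. For illustration, assume 5, 10 or 15 per 100 patient-years. Expected number = rate × 3.07, and the chance of at least one = 1 − exp(−expected).

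| Assumed rate per 100 patient-years | Expected SAEs in window | Chance that at least one occurs |
|---|---|---|
| 5 | 0.153 | 14.2% |
| 10 | 0.307 | 26.4% |
| 15 | 0.460 | 36.9% |

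These are chances that an SAE occurs, not that one is missed.

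**5. Effect of one missed patient**

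1/40 = 2.5%. Exact (Clopper-Pearson) 95% intervals: 0/40 gives 0 to 8.8%; 1/40 gives 0.06% to 13.2%. The intervals overlap heavily, and the plan sets no SAE threshold that the difference could cross.

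**The case against.** The strongest reply is that this is a deliberate choice: report everything, and reserve prolonged follow-up for related events. For a 16-week study of an approved drug in 40 patients, that is defensible. This stands to the extent that the protocol does not contradict itself, and the point is an improvement rather than a correction of an error.

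Several stronger readings are tempting, but the documents do not support them.

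- *Unrelated SAEs are lost, or their classification is frozen.* They are reported at once and their dates are tracked to the final exam. Upgrading is not forbidden, and an SAE upgraded to related comes under the follow-up rule and onto the DSMB's three-monthly list. A worsening that leads to death, prolonged hospital stay or lasting disability meets an SAE criterion itself, so it is arguably reportable within the window.
- *SAEs in the window are known only if the patient volunteers them.* The site must report them however it learns of them, and some patients may stay in contact through the continued drug supply foreseen in INTRODUCTION/BACKGROUND. Neither route is a planned safety contact.
- *Nobody is seen in the window.* This is shown for completers. An early terminator's final visit may fall inside it.
- *There is a 14% to 37% chance of missing an SAE.* That range rests on an assumed rate and concerns occurrence. It bounds the chance of a miss only if the assumed rate is right.

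Finally, the departmental SOPs cited in SAFETY MONITORING are not in the documents and may add follow-up. That cannot be checked. With three to four sites, it would not cure a restriction written into the shared protocol.

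**Conclusion.** The point holds in limited form. Pregnancies excepted, follow-up to outcome and re-assessment of relationship are required only for SAEs already judged related. For completers, the four-week window has no scheduled contact, so new SAEs there are found passively. Followed exactly, these rules give poorer data for the secondary objective.

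The size is small and cannot be estimated from the documents. The ceiling of 3.07 patient-years assumes that all 40 patients are uncovered throughout. The only rate the protocol provides gives about 0.02 events, for one SAE type and on the assumption that the week 52 rate carries over to the window. The number of SAEs affected by the follow-up rule cannot be given at all. The primary sPGA endpoint is not touched. The change is worth making because it is cheap; the trial does not depend on it.

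**What to change.** 1. In Follow-up reports, delete *related*, so that every SAE is followed until resolved or judged permanent, with its relationship re-assessed at each visit and by telephone after the last one.
2. Add one telephone contact to Appendix A, four weeks after the subject stops participation: counted from V6 for completers, and from the ET visit where that comes later than stopping. It should ask about new SAEs, update open ones, and record any brodalumab or other treatment since the last visit, so that events under post-trial treatment can be listed separately.
3. Send the DSMB later outcome information on any SAE. Upgrades to related already reach it through the three-monthly list.

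**Cost.** A short edit to one paragraph, one added column in the schedule and about 40 calls. The downsides are some follow-up past study end of unrelated SAEs still open, and some events found by the call that occurred under post-trial treatment and need separate listing.
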